# **13.2 WOMAC**

It consists of a questionnaire for specific assessment of the quality of life of patients with knee osteoarthritis. It is divided into three domains pain, stiffness and daily activities from 24 questions in which the patient has 5 response options (none, little, moderate, intense and very intense) and from the answers obtained has a score dividing the by the number of items in each of the domains.

#### 13.3 Pharmaceutical Care

It consists of evaluating the patients' pharmacological therapy, being able to collect data on the health situation, use of medications and dosages administered, as well as adverse reactions and possible drug interactions.

## 14. Statistical analysis

Statistical analysis will be performed in the SPSS program (Statistical Package for the Social Sciences, version 13.0). For the analysis, descriptive statistics will be performed, with measures of central tendency (mean, median and standard deviation), for variables that follow the normal distribution. Qualitative variables will be expressed in frequency and percentage. The difference will be analyzed by the chi-square test or Fischer test for the categorical variables and the Mann-Whitney and Student tests for the resulting variables. A statistically significant difference will be considered when p <0.05.

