# 1. Type of study

A randomized, blind-control clinical trial with paired samples will be conducted. Patients who meet the diagnostic criteria proposed by NICE (2014) with approximately 150 patients who agree to participate in the study and sign the Free and Informed Consent Term (Appendix A) will be elected.

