# 3. The size of the sample

The sample size of the patients was calculated considering the necessary amount of subjects to detect difference of at least 3 points in the pain perception through the visual analgesic scale (scale from 0 to 10), considering a significance level of 1% and test power of 95% in two-tailed hypothesis test, as well as the value of 4 for standard deviation (MATA et al., 2015). The sample was calculated in 126 patients and considering a sample loss around 20%, the number of subjects was 150, with 75 subjects in each sample (BENAZZI, FIGUEIREDO, BANASSI, 2010).

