## 7. Removal criteria

Patients will be removed when:

- Undergoing knee surgery during the course of the research.
- Subjected to joint infiltration with corticoids or any other type and medication of intraarticular use.
- Heat intolerant or other discomfort during exposure to sand.

For evaluation and follow-up of the volunteers will be carried out in parallel a work of pharmaceutical attention with monitoring of the use and frequency of medications, especially the use of analgesics and / or anti-inflammatories.

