#### 9. Intervention

Patients selected for the study will have their knee (s) affected by OA fully submerged in the beach sand 2 (two) times per week for 30 (thirty) minutes each session at the same location and at the same time of day.

The natural gamma (②) radiation doses of the monazite sands will be monitored in both groups through equipment that counts and accumulates the records for the desired time. In addition, the radiation measurements ② will be associated with the atmospheric and climatic measurements of each group. An interview with the patients will be performed initially (Appendix B), blood collected for analysis and applied to the Visual Analogue Scale (Annex C) and WOMAC (Annex D). The questionnaires as well as the blood collection for laboratory analysis will be repeated at the beginning of the study (day zero) and after 1, 2, 3, 6, 9 and 12 months for later analysis and comparison of the data.

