#### 10. Values evaluated

# 10.1 Primary outcome Measure:

Change pain perception through the visual analgesic scale of the volunteers (VAS)

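### The primary VAS outcome has six post-baseline visits but no decisive visit and no rule across visits, and the 5% test level is not reconciled with the 1% level used for sizing

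*Combined protocol and SAP*

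**What the plan says.** All references are to the combined protocol and SAP.

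- **Primary outcome (section 10.1).** The whole definition is "Change pain perception through the visual analgesic scale of the volunteers (VAS". It says change, but not change to when.
- **Visits (section 9).** The questionnaires, VAS included, "will be repeated at the beginning of the study (day zero) and after 1, 2, 3, 6, 9 and 12 months". That is a baseline and six later visits, all with the same status.
- **Analysis (section 14).** After chi-square or Fisher tests for categorical variables, the plan gives "the Mann-Whitney and Student tests for the resulting variables. A statistically significant difference will be considered when p <0.05". There is no visit, summary over visits, repeated-measures model, testing order or multiplicity rule. It does not say when each of the two tests applies, or whether they are two-sided.
- **Sizing (section 3).** The calculation targets a 3-point VAS difference with SD 4, "considering a significance level of 1% and test power of 95% in two-tailed hypothesis test". It arrives at 126 patients and then, "considering a sample loss around 20%, the number of subjects was 150, with 75 subjects in each sample".

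**The concern.** A primary analysis should be fixed before the data are seen: one variable, one time, one test, one level. Here the variable is given, but the time is not. With six visits open, the visit that carries the conclusion could be chosen after the results are known, and the error rate of a trial read that way is not the 5% of section 14.

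The level raises a second question. The sample size was built on 1% and the tests are to be read at 5%. A reader of the final report could not tell whether 5% was intended for the primary outcome or is a general default carried into section 14.

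**Working it through.** **1. Reproduce the plan's sample size.** Inputs from section 3: difference 3, SD 4, power 95%, two-sided 1%. Formula per group: n = 2 × (z_alpha + z_beta)² × SD² / difference².

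- At 1%: 2 × (2.576 + 1.645)² × 16/9 = 63.3 per group, 126.7 in total. The plan states 126, so the 1% level really was used.
- At 5%: 2 × (1.960 + 1.645)² × 16/9 = 46.2 per group, or 94 in total after rounding each group up to 47.

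**2. Power after losses.** Section 3 expects about 20% loss: 75 × 0.80 = 60 per group. Unadjusted t-test (noncentral t, 118 degrees of freedom, difference 3, SD 4):

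| Level | Power at 60 per group |
|---|---|
| 1% | 93.0% |
| 5% | 98.3% |

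**3. Where the two levels part.** Standard error of the difference = 4 × √(2/60) = 0.730. Smallest significant observed difference = critical t × 0.730:

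- 5%: 1.980 × 0.730 = 1.45 points
- 1%: 2.618 × 0.730 = 1.91 points

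A result between 1.45 and 1.91 is significant at 5% and not at 1%. The chance of a result on which the levels disagree is 5% − 1% = 4% with no true effect, and 98.3% − 93.0% = 5.3% if the true difference is the planned 3 points.

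**4. Six visits, any of which may count.** The documents give no between-visit correlation, so the values here are assumptions. The figure is the chance, with no true effect, that at least one of six two-sided tests is significant.

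*Equal correlation between the six test statistics (numerical integration):*

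| Correlation | Each test at 5% | Each test at 1% |
|---|---|---|
| 0.5 | 20.7% | 4.9% |
| 0.7 | 16.4% | 3.9% |
| 0.8 | 13.9% | 3.3% |
| 0.9 | 10.8% | 2.5% |

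*Correlation decaying with months apart (0.5 to 0.95 per month, simulated on the section 9 schedule), each test at 5%:*

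| Score tested | False-positive rate |
|---|---|
| Change from day 0 | about 21% to 18% |
| Visit value | about 25% to 13% |
| Baseline-adjusted | about 25% to 19% |

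In every case examined, the rate at 5% per visit is more than twice the nominal 5%.

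**5. Choice between Student and Mann-Whitney.** Taking whichever is significant at a single visit, with 60 per group and no true effect, moves 5% to 5.9% for normal data and 6.7% for an assumed skewed 0–10 score. This is minor beside the choice of visit.

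**The case against.** Several points on the other side are fair.

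- **Only section 14 sets a rule for significance.** The 1% in section 3 is a sizing input. A reader might infer that the plan has two competing success thresholds; it does not. Sizing at a stricter level than the test is conservative for power, and one test read at 5% keeps its 5% error. This stands. What remains is an unexplained inconsistency, and step 3 shows that the levels would seldom disagree if the effect were absent or as large as planned.
- **No section says that a significant result at any visit is a success.** A reader might infer that the trial has a false-positive rate of 11% to 25%. The documents do not support that as a property of the written plan: it is what follows if any visit may count, under assumed correlations. The defect is that nothing excludes that reading.
- **Month 12 may be implied by the one-year intervention.** That is plausible, but no section says it, and section 9 gives months 1 to 9 the same standing.
- **The 1% may have been meant as an allowance for six visits.** At 1% per visit the overall error would indeed be at or below about 5% in the equal-correlation cases. But no section says so, and section 14 does not test at 1%.
- **Section 10.1 already says change.** Section 14 is loosely worded, but the natural reading is that it tests the outcomes as section 10 defines them. The variable is not the gap.
- **The open choice of test matters little.** Step 5 confirms this. It is worth closing in the same edit, but it is not the ground for the point.

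**Conclusion.** The point holds in two parts of unequal weight.

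The main part is that the primary outcome has no decisive visit and no rule for six visits, so the plan does not fix which comparison decides the trial. No other section repairs this. Its possible size is a false-positive rate of about 11% to 21% under equal correlations of 0.9 to 0.5, or about 13% to 25% under decaying correlations, conditional on any visit being allowed to count.

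The lesser part is that the size rests on a two-sided 1% level while section 14 tests at 5%, without explanation. A reader might infer that the trial is too small. It is not: under the plan's own difference, SD and loss, power is at least 93.0% at either level. The consequence is confined to observed differences between 1.45 and 1.91 points (60 per group, SD 4).

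This should be settled before any unblinded comparison, because it determines what the primary result is.

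**What to change.** In section 14:

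1. Name one primary contrast, for example the between-arm difference in VAS change from day 0 to month 12, the end of the one-year intervention.
2. Name one estimator adjusted for baseline VAS. ANCOVA at month 12 is enough; a mixed model over the six visits that reports the month-12 contrast is an acceptable alternative. It replaces the open Student/Mann-Whitney choice for the primary outcome, with Mann-Whitney on month-12 change as a sensitivity analysis. Baseline adjustment is proposed for precision; an unadjusted test of month-12 change would also be valid.
3. State that the other visits are supportive and cannot establish primary success.
4. State the missing-data assumption for patients lost or removed. Section 7 removes patients for reasons such as "Undergoing knee surgery during the course of the research", which may be related to pain.

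In sections 3 and 14, state the same two-sided level: either test the primary outcome at 1%, or keep 5% and restate the basis of section 3.

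The cost is wording only. Baseline VAS and all visits are already collected, and enrolment need not change. There are three downsides. An effect seen only at an early visit would be supportive. Keeping 1% means 93.0% rather than 98.3% power at 60 per group. Either estimator depends on an assumption about missing month-12 values that the data cannot fully check.

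### The primary comparison of VAS pain makes no use of the day-zero score as a covariate, so it is valid but less precise than it could be at no extra cost

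*Combined protocol and SAP*

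**What the plan says.** All references are to the combined protocol and SAP.

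- Section 10.1 makes change in VAS pain the primary outcome. It names no visit.
- Section 9 schedules the questionnaires, VAS included, at baseline and at six follow-ups: they "will be repeated at the beginning of the study (day zero) and after 1, 2, 3, 6, 9 and 12 months".
- Section 14 analyses numeric outcomes by "the Mann-Whitney and Student tests for the resulting variables", with significance at p below 0.05. It does not say whether change or the follow-up score is tested. No covariate, regression, ANCOVA or mixed model appears anywhere, and no stratification by baseline pain is described.
- Section 3 sizes the trial for a "difference of at least 3 points in the pain perception", "considering a significance level of 1% and test power of 95% in two-tailed hypothesis test", with "the value of 4 for standard deviation". It does not say whether that SD is for a single score or for a change. The result is 126 patients, raised to 150 (75 per group) for losses.

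**The concern.** Where a baseline value of the primary outcome exists for every patient, it usually explains part of the variation at follow-up. A two-sample test on the follow-up score ignores it. A two-sample test on change subtracts all of it, which over-corrects whenever r is below 1. ANCOVA estimates how much to subtract.

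The stakes are the width of the confidence interval around the treatment difference, the part of any chance baseline difference between the two beaches that stays in the result and, under some readings of section 3, the power. The section 3 ambiguity matters because, if 4 is the SD of a score, the SD of the change exceeds 4 whenever r is below 0.5.

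**Working it through.** **Inputs.** Difference 3 points, SD 4, two-sided alpha 1%, power 95%, 126 patients or 63 per arm (section 3); alpha 5% (section 14). Assumptions: r from 0.3 to 0.7, equal variances at both visits, and a common slope in both arms.

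**1. The plan's own figure.** n per arm = 2 × 4² × (2.576 + 1.645)² / 3² = 63.3, or 126.7 in total. The stated 126 therefore comes from an unadjusted comparison of two independent means. At 63 per arm the power is 94.9% by the normal formula and 94.3% by the t test.

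**2. Variances.** With score variance σ²:

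- unadjusted change: 2(1 − r)σ²
- unadjusted follow-up score: σ²
- ANCOVA: (1 − r²)σ²

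ANCOVA relative to change is (1 + r)/2; relative to the follow-up score it is 1 − r².

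| r | Reduction against change | Reduction against follow-up score |
|---|---|---|
| 0.3 | 35% | 9% |
| 0.5 | 25% | 25% |
| 0.7 | 15% | 49% |

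**3. Power if 4 is the SD of a single score** (noncentral t, 63 per arm, 3 points). The SD of change is 4√(2(1 − r)) = 4.73, 4.00, 3.10 for r = 0.3, 0.5, 0.7. The ANCOVA residual SD is 4√(1 − r²) = 3.82, 3.46, 2.86.

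| r | Change, 1% | ANCOVA, 1% | Change, 5% | ANCOVA, 5% |
|---|---|---|---|---|
| 0.3 | 82.5% | 96.2% | 94.2% | 99.2% |
| 0.5 | 94.3% | 98.7% | 98.7% | 99.8% |
| 0.7 | 99.7% | 99.9% | about 100% | about 100% |

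If the follow-up score is tested instead, its SD is 4 whatever r is, and unadjusted power is 94.3% at 1% and 98.7% at 5%.

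**4. Power if 4 is the SD of change.** Unadjusted power is 94.3% at 1%. The ANCOVA residual SD is 4√((1 + r)/2) = 3.22, 3.46, 3.69, giving 99.5%, 98.7% and 97.3% at 1%.

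**5. Confidence interval.** With score SD 4, r = 0.3 and 63 per arm, the 95% half-width is about 1.67 points for change and 1.35 for ANCOVA.

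**6. Chance baseline difference.** With score SD 4 and 63 per arm, its standard error is 4√(2/63) = 0.71 points. A test on change leaves a fraction (1 − r) of it in the result, and a test on the follow-up score leaves r. At r = 0.5, a baseline difference of one standard error shifts either result by 0.5 × 0.71 = 0.36 points, or 12% of the 3-point target. ANCOVA removes this shift.

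**The case against.** The strongest reply is that nothing here is an error. Randomization protects the type I error of the unadjusted tests, and their estimates are unbiased on average. Section 3 sizes the trial for the kind of two-group comparison that section 14 plans, so on this point the plan is consistent with itself. That stands: the issue is efficiency, not validity.

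Three stronger readings are tempting, and the documents do not support them.

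- *The trial is underpowered.* This needs three things together: 4 is a score SD, r is below 0.5, and change is tested at 1%. Section 3 does not settle the first, the documents give no value of r, and section 14 does not say that change is what is tested and sets 5%, not 1%. At 5% the 82.5% becomes 94.2%; at r = 0.7 there is no shortfall even at 1%. A score SD of 4 is also close to the largest possible on a 0 to 10 scale, which is about 5, so that branch is near the worst case.
- *All of any baseline imbalance stays in the result.* A change score leaves only (1 − r) of it, and a follow-up score only r.
- *Change is definitely what the tests compare.* Section 10.1 suggests so, but section 14 leaves it open. The criticism applies either way, with a different variance ratio.

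It is also fair to say that the missing primary visit and the 1% against 5% levels are more basic matters. They are separate points, but a visit must be named before a single-visit ANCOVA can be specified.

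**Conclusion.** The point holds as a loss of precision that can be avoided for nothing. For r between 0.3 and 0.7, adjustment for day-zero VAS cuts the variance by 35% to 15% against unadjusted change, or by 9% to 49% against the unadjusted follow-up score, and it removes the residual chance baseline difference. These reductions do not depend on the significance level or on what the SD of 4 describes. They do rest on an assumed r and on equal variances.

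The consequence for power is conditional and mostly modest. Over the range of r examined, ANCOVA keeps power above 95% under either reading of the SD, while the unadjusted test on change falls clearly below it in only one corner of the assumptions. The change is worth making, but the planned tests would not give an invalid result.

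**What to change.** In section 14, make the primary analysis a linear model of VAS at one named follow-up visit, with arm and day-zero VAS as terms; or a mixed model over the six follow-up visits with the same baseline term and a stated contrast between arms. Report the adjusted mean difference with its confidence interval, beside the 3-point target. Use the same baseline-adjusted model for WOMAC. Keep the Student and Mann-Whitney tests as sensitivity analyses.

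In section 3, add a sentence saying whether the SD of 4 is for a single score or for a change.

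The cost is a few lines of text. The model can be fitted in SPSS, the baseline scores are already scheduled, and no new data or patients are needed. The change should be fixed before outcome data by arm are examined.

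### The sample size is set at a two-sided 1% level, but the only decision rule is p < 0.05, and nothing reconciles the two

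*Combined protocol and SAP*

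**What the plan says.** All references are to the combined protocol and SAP.

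- **Section 3 (sample size).** The calculation targets a difference of at least 3 points on the 0 to 10 pain scale, "considering a significance level of 1% and test power of 95% in two-tailed hypothesis test", "as well as the value of 4 for standard deviation". It arrives at 126 patients, raised to 150 for loss of about 20%, "with 75 subjects in each sample".
- **Section 10.1 (primary outcome).** The primary outcome is change in VAS pain, so section 3 sizes the trial on the primary variable.
- **Section 14 (statistical analysis).** After naming chi-square or Fisher tests for categorical variables and Mann-Whitney and Student tests for the others, it closes with a single rule: "A statistically significant difference will be considered when p <0.05". The rule names no outcome, exempts none, and does not say whether the p-value is two-sided.

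No section contains an alpha allocation, a multiplicity rule or a separate threshold for the primary outcome that would explain why two levels appear.

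**The concern.** The alpha for the primary test is one of the few numbers that fixes what the trial's main claim means. Here the documents give two. Section 3 justifies the number of patients at a 1% false-positive rate. Taken literally, section 14 runs the test at 5%, five times that rate.

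The practical exposure is a primary result with p between 0.01 and 0.05. Under section 14 it is positive; by the level on which the sample size was justified it is not. If the choice of level is left open until the data are in, it can be made, or be suspected of having been made, to suit the result.

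**Working it through.** **Inputs.** From section 3: difference 3, SD 4, two-sided alpha 0.01, power 0.95, equal groups. From section 14: alpha 0.05, taken here as two-sided because section 14 is silent on this. Evaluable patients per group: 60 (75 less 20%), 63 (half of 126) and 75 (no loss).

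**Step 1: which level produced 126?** For two independent means with equal groups, the normal approximation to the total is

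N = 4 × (z₁₋α/₂ + z₀.₉₅)² × SD² / difference²

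- Two-sided 1%: 4 × (2.576 + 1.645)² × 16/9 = 4 × 17.814 × 1.778 = **126.7**, against the stated 126.
- Two-sided 5%: 4 × (1.960 + 1.645)² × 16/9 = 4 × 12.995 × 1.778 = **92.4**.

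Other readings also miss 126: one-sided 1% gives 114, one-sided 5% gives 78, and a paired test at two-sided 1% gives about 36 in all. The 1% was therefore used in the calculation and is not a misprint for 5%.

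**Step 2: power for 3 points at each level.** Noncentral t, with 2n − 2 degrees of freedom and noncentrality 3 / (4√(2/n)):

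| Evaluable per group | Power at 1% | Power at 5% |
|---|---|---|
| 60 | 93.0% | 98.3% |
| 63 | 94.3% | 98.7% |
| 75 | 97.5% | 99.5% |

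A 5% test reaches about 95% power with 47 to 48 per group (94.9% and 95.3%), that is 94 to 96 evaluable in total, against 126.

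**Step 3: which observed differences get opposite verdicts?** The smallest significant difference is t₁₋α/₂ × 4 × √(2/n). For n = 63 the standard error is 4 × √(2/63) = 0.713, so the cut-offs are 1.979 × 0.713 = 1.41 at 5% and 2.616 × 0.713 = 1.86 at 1%.

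| Evaluable per group | Cut-off at 5% | Cut-off at 1% |
|---|---|---|
| 60 | 1.45 | 1.91 |
| 63 | 1.41 | 1.86 |
| 75 | 1.29 | 1.70 |

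**Step 4: how often would the verdict depend on the level?** This is power at 5% minus power at 1%. With 63 per group:

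| True difference (points) | Probability that 0.01 < p < 0.05 |
|---|---|
| 0 | 4.0% |
| 1.0 | 16.9% |
| 1.6 | 24.6% |
| 2.0 | 21.9% |
| 2.5 | 12.4% |
| 3.0 | 4.4% |

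At 3 points the figure is 5.3% with 60 per group and 2.0% with 75.

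**The case against.** The best defence is that there is no real ambiguity. Section 3 explains how the number of patients was reached and does not say that results will be judged at 1%. Section 14 says how they will be judged. Planning at a stricter level than the test is conservative: it buys a larger trial, and at 5% the 95% power target is met with room to spare. At the two scenarios the documents support, no effect and 3 points, the level changes the verdict only about 4% of the time. The 25% figure needs a true difference of 1.6 points, which the documents do not mention and which lies close to the peak.

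Much of this is fair. The trial is not underpowered, and the 25% is close to a worst case. A deliberate choice to size at 1% and test at 5% would be acceptable, but the plan does not say that it made one. Without that statement, section 3's alpha does not describe the test that section 14 prescribes, and a reader cannot tell a conservative design from an oversight.

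Two further objections stand as limits on the figures. Section 1 mentions paired samples, whereas the calculations assume two independent groups; the 75 per group and the match to 126 support independence. Section 3 also does not say whether SD 4 refers to a change or to a single score. Separately, section 10.1 names no primary time point among the repeated assessments in section 9. One alpha will not fully define the primary test until that is settled, but this is a different point.

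**Conclusion.** The inconsistency is real. The stated 126 comes from a two-sided 1% level, the only decision rule is p < 0.05, and nothing links them. It does not threaten power for the planned 3 points. Its effect is on the standard of evidence: nominal false-positive rate 1% or 5%, with observed differences of about 1.4 to 1.9 points at 60 to 63 per group receiving opposite verdicts.

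These sizes rest on SD 4, two independent equal groups and a two-sided Student test. If Mann-Whitney is used for VAS, which section 14 allows, the two levels still conflict but no such cut-off in mean points applies. This should be fixed but is not fatal.

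**What to change.** Before results are known, state one two-sided alpha for the primary VAS comparison and make sections 3 and 14 agree. The documents do not show which level was intended, so the sponsor must choose.

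- **Option (a): 1% for the primary outcome.** Add to section 14: *The primary VAS comparison is tested at two-sided alpha = 0.01, as in section 3; two-sided 0.05 applies to the other outcomes.* The cost is a stricter primary threshold, with power of 93.0% at 60 evaluable per group or 94.3% at 63, slightly below the stated 95%.
- **Option (b): 5% throughout.** Keep 0.05 in section 14 and add that it is two-sided. In section 3, keep the record that 126 was derived at 1%, and add that the test will be at two-sided 0.05, where 60 to 63 evaluable per group give about 98 to 99% power for 3 points with SD 4. The cost is an error level openly less strict than the one used for planning.

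Either option takes one or two sentences and no extra patients.
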